5.3.1.4.2 Management of Proteinuria

Regular assessment for proteinuria should be conducted as detailed in the Study Flow Chart (Section 6.0). Guidelines for assessment and management of proteinuria are summarized as follows:

- If proteinuria $\geq 2+$ is detected on urine dipstick testing, study drug will be continued and a 24-hour urine collection for total protein will be obtained as soon as possible within 72 hours to verify the grade of proteinuria. Grading according to the National Cancer Institute's (NCI) Common Terminology Criteria for Adverse Events (CTCAE v4.03) will be based on the 24 hour urinary protein result. Management of lenvatinib administration will be based on the grade of proteinuria according to the Dose Reduction and Interruption Instructions provided in Table 8.

Table 8: Dose Modification Guidelines for Lenvatinib-Related Adverse Events

Treatment-Related Toxicity ^{a,b}	During therapy	Adjusted Dose
Grade 1		
Continue treatment		
Intolerable Grade 2^c		
First occurrence	Interrupt until resolved to Grade 0-1 or baseline	No change
Second occurrence (same toxicity or new toxicity)	Interrupt until resolved to Grade 0-1 or baseline	14 mg orally once a day
Third occurrence(same toxicity or new toxicity)	Interrupt until resolved to Grade 0-1 or baseline	10 mg orally once a day
Grade 3		
First occurrence	Interrupt until resolved to Grade 0-1 or baseline	14 mg orally once a day
Second occurrence (same toxicity or new toxicity)	Interrupt until resolved to Grade 0-1 or baseline	10 mg orally once a day
Third occurrence (same toxicity or new toxicity)	Interrupt until resolved to Grade 0-1 or baseline	8 mg orally once a day
Fourth occurrence (same toxicity or new toxicity)	Interrupt until resolved to Grade 0-1 or baseline	Discuss with Sponsor
Grade 4^d		
Discontinue Study Treatment		

a: A delay of study treatment for more than 28 days (due to treatment-related toxicities) will require a discussion with the sponsor before treatment can be resumed.

b: Initiate optimal medical management for nausea, vomiting, and/or diarrhea prior to any study treatment interruption or dose reduction.

c: Applicable to any grade 2 proteinuria and to Grade 2 toxicities judged by the subject and physician to be intolerable.

d: Excluding laboratory abnormalities judged to be non-life-threatening, in which case manage as Grade 3.

5.3.2 Timing of Dose Administration

Trial treatment should be administered on Day 1 of each cycle after all procedures/assessments have been completed as detailed on the Trial Flow Chart (Section 6.0). Trial treatment may be administered up to 3 days before or after the scheduled Day 1 of each cycle due to administrative reasons.

All trial treatments will be administered on an outpatient basis.

Pembrolizumab 200 mg will be administered as a 30 minute IV infusion every 3 weeks. Sites should make every effort to target infusion timing to be as close to 30 minutes as possible. However, given the variability of infusion pumps from site to site, a window of -5 minutes and +10 minutes is permitted (i.e., infusion time is 30 minutes: -5 min/+10 min).

The Pharmacy Manual contains specific instructions for the preparation of the pembrolizumab infusion fluid and administration of infusion solution.

5.3.3 Trial Blinding/Masking

This is an open-label trial; therefore, the Sponsor (NYU Langone Medical Center), investigator and subject will know the treatment administered.

5.4 Concomitant Medications and Vaccinations Allowed and Prohibited

Medications or vaccinations specifically prohibited in the exclusion criteria are not allowed during the ongoing trial. If there is a clinical indication for one of these or other medications or vaccinations specifically prohibited during the trial, discontinuation from trial therapy or vaccination may be required. The investigator should discuss any questions regarding this with the Merck Clinical team. The final decision on any supportive therapy or vaccination rests with the investigator and/or the subject's primary physician.

5.4.1 Acceptable Concomitant Medications

All treatments that the investigator considers necessary for a subject's welfare may be administered at the discretion of the investigator in keeping with the community standards of medical care. All concomitant medication will be recorded on the case report form (CRF) including all prescription, over-the-counter (OTC), herbal supplements, and IV medications and fluids. If changes occur during the trial period, documentation of drug dosage, frequency, route, and date may also be included on the CRF.

All concomitant medications received within 28 days before the first dose of trial treatment and 30 days after the last dose of trial treatment should be recorded. Concomitant medications administered after 30 days after the last dose of trial treatment should be recorded for serious adverse events (SAEs) and events of clinical interest (ECIs) as defined in Section 7.2.

5.4.2 Prohibited Concomitant Medications

Subjects are prohibited from receiving the following therapies during the Screening and Treatment Phase (including retreatment for post-complete response relapse) of this trial:

- Antineoplastic systemic chemotherapy or biological therapy
- Immunotherapy not specified in this protocol
- Chemotherapy not specified in this protocol
- Investigational agents other than pembrolizumab and lenvatinib
- Radiation therapy
 - Note: Radiation therapy to a symptomatic solitary lesion or to the brain may be allowed at the investigator's discretion.
- Live vaccines within 30 days prior to the first dose of trial treatment and while participating in the trial. Examples of live vaccines include, but are not limited to, the following: measles, mumps, rubella, varicella/zoster, yellow fever, rabies, BCG, and typhoid vaccine.

- Systemic glucocorticoids for any purpose other than to modulate symptoms from an event of clinical interest of suspected immunologic etiology. Replacement therapy (e.g., physiologic corticosteroid replacement therapy for adrenal or pituitary insufficiency, etc.) is not considered a form of systemic treatment and is allowed with dosing not to exceed 10mg daily of prednisone equivalent.

Subjects who, in the assessment by the investigator, require the use of any of the aforementioned treatments for clinical management should be removed from the trial. Subjects may receive other medications that the investigator deems to be medically necessary.

The Exclusion Criteria describes other medications which are prohibited in this trial.

There are no prohibited therapies during the Post-Treatment Follow-up Phase.

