7.1.2.5 Tumor Imaging and Assessment of Disease

Tumor assessments will be based on RECIST v1.1 and will be performed according to the schedule presented in Sections 6.0 and 7.0. Tumor assessments should include the following evaluations: physical examination and CT of chest, abdomen, and pelvis. The preferred method of disease assessment is CT with contrast. If CT with contrast is contraindicated, CT without contrast is preferred over MRI. The same method is preferred for all subsequent tumor assessments.

Measurability of Tumor Lesions

Tumor lesions will be categorized as follows:

- **Measurable Lesions** - Must be accurately measured in at least one dimension (longest diameter in the plane of measurement is to be recorded) with a minimum size of:

Product: Pembrolizumab

Protocol/Amendment No.: May 18, 2020v2.0

- 10 mm by CT scan (irrespective of scanner type) and MRI (no less than double the slice thickness and a minimum of 10 mm)
- 10 mm caliper measurement by clinical exam (when superficial)
- Malignant lymph nodes are considered pathologically enlarged and measurable, a lymph node must be ≥ 15 mm in short axis when assessed by CT scan (CT scan slice thickness recommended to be no greater than 5 mm)
- **Nonmeasurable Lesions** - Nonmeasurable lesions are defined as all other lesions (or sites of disease), including small lesions (longest diameter < 10 mm or pathological lymph nodes with ≥ 10 to < 15 mm in short axis). Lesions considered truly nonmeasurable include the following: leptomeningeal disease, ascites, pleural/pericardial effusion, and inflammatory breast disease, lymphangitic involvement of skin or lung, abdominal masses/abdominal organomegaly identified by physical exam that is not measurable by reproducible imaging techniques.
- **Target Lesions** - All lesions up to a maximum of 5 lesions total (and a maximum of 2 lesions per organ) representative of all involved organs should be identified as target lesions. It may be the case that, on occasion, the largest lesion does not lend itself to reproducible measurement in which circumstance the next largest lesion which can be measured reproducibly should be selected.
- **Non-target Lesions** - It is possible to record multiple non-target lesions involving the same organ as a single item on the case report form (e.g., “multiple enlarged pelvic lymph nodes” or “multiple liver metastases”).

Evaluation of Target Lesions

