8.0 STATISTICAL ANALYSIS PLAN

8.1 Statistical Analysis Plan

The Simon optimal two-stage design to test the null hypothesis of <10% RR (CR+PR) versus the alternative hypothesis of >30% overall response rate requires an overall sample size of 29 subjects in order to achieve 80% power with a significance level of 5%. After testing the combination therapy on 10 response evaluable subjects in the first stage, the trial will be terminated if there are 1 or fewer responses. If there are 2 or more responses (including non-confirmed responses) the trial will continue on to second stage. A response evaluable subject is defined as having received both investigational agents for at least 2 cycles and had one CT scan for disease evaluation on therapy, or evidence of early (prior to 2 cycles) clear progression on physical examination, or death prior to 2 cycles. Best overall response for the interim analysis will be assessed up to 6 months on treatment. If the trial goes on to the second stage, then if there are 5 or fewer responses out of 29 response evaluable subjects, the combination therapy will be rejected. If there are 6 or more responses (including non-confirmed responses) over the entire treatment duration - the combination will be studied further.

At the end of the study, toxicities, as measured by the NCI CTCAE Version 4.03, will be described by frequency and grade, by cycle and over all cycles, with the maximum grade over all cycles used as the summary measure per patient. Overall response rates (defined as PR plus CR) will be estimated with exact 95% confidence intervals. PFS and OS will be described using Kaplan-Meier curves.

All subjects who receive at least one dose of the lenvatinib and/or pembrolizumab combination will be evaluable for toxicity.

Efficacy Measures

Response rate (RR): Best overall response will be calculated as the best response (CR or PR) recorded from the start of treatment for each subject, and will be used for the summaries of objective response. Best overall response will be determined programmatically based on the RECIST 1.1 criteria. For this study confirmation of response within 4 weeks will not be required.

Progression Free Survival (PFS): is defined as the interval between the date of start of treatment and the earlier date of objective disease progression per RECIST 1.1 criteria or death due to any cause in the absence of progression.

Product: Pembrolizumab/MK-3475

Protocol/Amendment No.: May 18, 2020v2.0

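### On-study radiotherapy may be given to a target lesion, and nothing in the response rules stops the resulting shrinkage from counting as a PR toward the 2/10 and 6/29 decision rules

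*Combined protocol and SAP*

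**What the plan says.** **Radiotherapy.** Section 5.4.2 lists radiation among the therapies prohibited during screening and treatment, then adds a note: "Radiation therapy to a symptomatic solitary lesion or to the brain may be allowed" at the investigator's discretion. The note does not say whether the lesion may be a target lesion. Below the list, the same section says that subjects who need any of the listed treatments should be removed from the trial. Section 5.4 says that discontinuation from trial therapy may be required.

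**Response.** Measurable disease is an entry criterion (Section 5.1.2). Section 7.1.2.5 takes as targets "All lesions up to a maximum of 5 lesions total (and a maximum of 2 lesions per organ". PR is a fall of at least 30% from baseline in the sum of target diameters. Neither the lesion rules nor the overall-response table in that section mentions a lesion irradiated on study.

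**Analysis.** Section 8.1 states: "Best overall response will be determined programmatically based on the RECIST 1.1 criteria". The best CR or PR from the start of treatment is used and confirmation is not required. The final rule counts responses over the whole treatment period. The design "requires an overall sample size of 29 subjects": stop at 1 or fewer responses in 10, reject at 5 or fewer in 29. Neither the response-evaluable definition nor the best-response definition refers to radiotherapy.

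**The concern.** The permission allows a local treatment that can itself shrink the lesion being measured. A program given only diameters cannot separate radiation effect from drug effect, and the plan does not tell it to try. For the response rate the error can run only upward, and a single-arm trial has no control group in which it would show.

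Both decision rules are exposed. Stage 1 continues on 2 responses in 10, stage 2 succeeds on 6 in 29, and unconfirmed responses count in each. One misattributed PR adds 1/29 = 3.4 percentage points to the final response rate and is one sixth of the responses needed for a go. PFS uses the same measurements, so local control of an irradiated target could also delay the 20% increase that defines progression.

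**Working it through.** **1. Inputs.** From Section 8.1: null rate 10%, alternative 30%, significance level 5%, power 80%, stage 1 n = 10 (continue if 2 or more respond), total N = 29 (go if 6 or more respond). From Section 7.1.2.5: the PR threshold of a 30% fall in the target sum. The number of subjects with a radiation-only response is **not** in the documents. One and two are assumptions, and a range of rates is shown in step 5.

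**2. The plan's own figures.**

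P(go | p) = Σ over x = 2..10 of P[Bin(10, p) = x] × P[Bin(19, p) ≥ 6 − x]

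At p = 0.10:

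| Stage 1 responses x | P(x) | P(enough in stage 2) | Product |
|---|---|---|---|
| 2 | 0.1937 | 0.1150 | 0.0223 |
| 3 | 0.0574 | 0.2946 | 0.0169 |
| 4 | 0.0112 | 0.5797 | 0.0065 |
| 5 | 0.0015 | 0.8649 | 0.0013 |
| 6 or more | 0.0001 | 1.0000 | 0.0001 |
| Total | | | **0.0471** |

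At p = 0.30 the sum is 0.805. A grid search over designs with alpha ≤ 0.05 and power ≥ 0.80 returns 1/10, 5/29 as the Simon optimal design. The stated design is right, but it has little slack: exact alpha passes 0.05 once the effective null rate exceeds about 10.15%.

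**3. When irradiation of one lesion can produce a PR.** Let the irradiated lesion make up a share s of the baseline target sum and shrink by a fraction f, with the other targets unchanged. The sum falls by s × f, so a PR needs s × f ≥ 0.30.

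- Sole target (s = 1): f ≥ 0.30 is enough. If it had first grown 10%, it must then fall by 1 − 0.70/1.10 = 36%.
- Three equal non-nodal targets (s = 0.33): a PR only if the lesion all but disappears.
- Four or five equal non-nodal targets (s = 0.25 or 0.20): complete disappearance gives a 25% or 20% fall, which is not a PR.

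The subject must also have no new lesion and no non-target progression. The route is therefore real but confined to a sole or dominant target.

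**4. Effect of k certain radiation-only responders at a true rate of 10%.** Fix k subjects as responders and leave the rest binomial.

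- One in stage 2: Σ over x = 2..10 of P[Bin(10, 0.1) = x] × P[Bin(18, 0.1) ≥ 5 − x] = **0.094**
- One in stage 1: Σ over x = 1..9 of P[Bin(9, 0.1) = x] × P[Bin(19, 0.1) ≥ 5 − x] = **0.128**
- Average over random placement: (19/29)(0.0942) + (10/29)(0.1285) = **0.106**

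| Two responders | P(go) | Placement weight |
|---|---|---|
| Both in stage 2 | 0.161 | 342/812 |
| One in each stage | 0.244 | 380/812 |
| Both in stage 1 | 0.282 | 90/812 |
| Average | **0.213** | |

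The interim look moves too. With one such subject in stage 1, the chance of continuing rises from 1 − 0.736 = 0.264 to 1 − 0.9⁹ = 0.613.

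**5. Range by rate.** Suppose instead that a proportion q of subjects who would not otherwise respond become PRs through radiation. The effective null rate is 0.10 + 0.90q:

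| q | Effective null rate | P(go) |
|---|---|---|
| 0 | 0.100 | 0.047 |
| 1% | 0.109 | 0.066 |
| 2% | 0.118 | 0.089 |
| 5% | 0.145 | 0.181 |
| 10% | 0.190 | 0.384 |

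**The case against.** **The subject would be removed anyway.** This is the best objection. Radiation is on the prohibited list, and Section 5.4.2 says that subjects needing a listed treatment should leave the trial. If that sentence governs, the subject goes and the problem largely disappears. But applied to the excepted radiotherapy it would cancel the exception, and the text does not say which prevails. Section 5.7 does not name radiotherapy among the mandatory reasons to stop treatment. Section 7.1.1.5.3 concerns new therapy started after the last dose of trial treatment. None of these says that a response recorded after radiotherapy is discarded. What stands is that the finding is conditional on the subject remaining on study.

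**Published RECIST 1.1 may cover it.** Sections 8.1 and 13.3 adopt the guideline, and Section 7.1.2.5 may not reproduce all of it. The guideline was not available for this review, so no rule is assumed from it in either direction. Even with such a rule, a programmatic derivation needs to know which lesion was irradiated and when. Section 5.4.1 lists medications and fluids for the CRF, and no radiotherapy item is described.

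**The event may be rare.** This stands. The figures are conditional on an assumed number of cases and do not predict that any will occur.

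**The brain exception adds little.** This also stands. Known active CNS metastases are excluded, scheduled imaging covers chest, abdomen and pelvis, and new lesions already count as progression.

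**Conclusion.** The point holds as a gap in the definition of the primary endpoint, joined to an unreconciled contradiction in Section 5.4.2. If a subject stays on study after radiotherapy to a sole or dominant target lesion, the rules as written can count the resulting shrinkage toward both decision thresholds. On the assumption of one certain radiation-only responder and a true rate of 10%, the false-go probability is 9.4% to 12.8% (average 10.6%) against a planned 4.7%. With two it is 16.1% to 28.2% (average 21.3%).

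Three stronger readings are not supported:

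- A reader might infer that any irradiated target that shrinks by 30% makes a responder. The criterion applies to the target sum against baseline, so this is true only for a sole target, or where the other targets also shrink.
- A reader might infer that response rate and PFS will be inflated. The documents give no frequency of on-study radiotherapy, so this is a possibility and not an expected result. PFS is only described by Kaplan-Meier curves, and no decision depends on it.
- A reader might infer that the sample size is wrong. It reproduces exactly.

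**What to change.** 1. **Section 5.4.2:** the sponsor reconciles the radiotherapy exception with the removal sentence. Which clinical rule applies is for the sponsor to decide; the items below concern only counting.
2. **CRF:** record site, date and target or non-target status of any on-study radiotherapy.
3. **Section 8.1, with a cross-reference in 7.1.2.5:** state that once a target lesion has been irradiated on study, later assessments cannot establish a CR or PR for the primary analysis. Best response then comes from assessments before radiotherapy, and the subject stays in the denominator. Apply this at the interim and final looks.
4. **Response sensitivity analysis:** count all recorded responses, including those after radiotherapy.
5. **PFS:** keep progression and death from any cause as events under the existing definition, and add a sensitivity analysis for subjects with target-lesion radiotherapy. Censoring at radiotherapy should not become the primary rule: it could discard later deaths, and a lesion becoming symptomatic is plausibly informative. No separate progression rule for brain lesions is needed.

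The cost is a few sentences and one CRF item. With radiation-only responses excluded, the design keeps alpha 0.047 and power 0.805 at N = 29. The downside is small: a genuine response first seen after target-lesion radiotherapy is not counted in the primary analysis, though it appears in the sensitivity analysis.

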5.5 Rescue Medications and Supportive Care

5.5.1 Supportive Care Guidelines

Subjects should receive appropriate supportive care measures as deemed necessary by the treating investigator. Suggested supportive care measures for the management of adverse events with potential immunologic etiology are outlined below. Where appropriate, these guidelines include the use of oral or intravenous treatment with corticosteroids as well as additional anti-inflammatory agents if symptoms do not improve with administration of corticosteroids. Note that several courses of steroid tapering may be necessary as symptoms may worsen when the steroid dose is decreased. For each disorder, attempts should be made to rule out other causes such as metastatic disease or bacterial or viral infection, which might require additional supportive care. The treatment guidelines below are intended to be applied when the investigator determines the events to be related to pembrolizumab.

Note: if after the evaluation the event is determined not to be related, the investigator does not need to follow the treatment guidance (as outlined below). Refer to Section 5.3.1.3 for dose modification.

It may be necessary to perform conditional procedures such as bronchoscopy, endoscopy, or skin photography as part of evaluation of the event.

Table 9: Dose Modification & Toxicity Management Guidelines for Immune Related AE's Associated with Pembrolizumab

General instructions:					
Immune-related AEs	Toxicity grade or conditions (CTCAEv4.0)	Action taken to pembrolizumab	irAE management corticosteroid and/or other therapies	Monitor and follow-up	
Pneumonitis	Grade 2	Withhold	
 Administer corticosteroids (initial dose of 1-2 mg/kg prednisone or equivalent) followed by taper 	
 Monitor subjects for signs and symptoms of pneumonitis Evaluate subjects with suspected pneumonitis with radiographic imaging and initiate corticosteroid treatment Add prophylactic antibiotics for opportunistic infections 	
	Grade 3 or 4, or recurrent grade 2	Permanently discontinue		
 Monitor subjects for signs and symptoms of enterocolitis (i.e. diarrhea, abdominal pain, blood or mucus in stool with or without fever) and of bowel perforation (i.e. peritoneal signs and ileus). Subjects with \geq Grade 2 diarrhea suspecting colitis should consider GI consultation and performing endoscopy to rule out colitis. Subjects with diarrhea/colitis should be advised to drink liberal quantities of clear fluids. If sufficient oral fluid intake is not feasible, fluid and electrolytes should be substituted via IV infusion. 	
Diarrhea / colitis	Grade 2 or 3	Withhold	
 Administer corticosteroids (initial dose of 1-2 mg/kg prednisone or equivalent) followed by taper 		
	Grade 4	Permanently discontinue			

General instructions:				
Immune-related AEs	Toxicity grade or conditions (CTCAEv4.0)	Action taken to pembrolizumab	irAE management with corticosteroid and/or other therapies	Monitor and follow-up
AST / ALT elevation or Increased Bilirubin	Grade 2	Withhold	
 Administer corticosteroids (initial dose of 0.5-1 mg/kg prednisone or equivalent) followed by taper 	
 Monitor with liver function tests (consider weekly or more frequently until liver enzyme value returned to baseline or is stable)
	Grade 3 or 4	Permanently discontinue	
 Administer corticosteroids (initial dose of 1-2 mg/kg prednisone or equivalent) followed by taper 	
Type 1 diabetes mellitus (T1DM) or Hyperglycemia	Newly onset T1DM or Grade 3 or 4 hyperglycemia associated with evidence of β -cell failure	Withhold	
 Initiate insulin replacement therapy for subjects with T1DM Administer anti-hyperglycemic in subjects with hyperglycemia 	
 Monitor subjects for hyperglycemia or other signs and symptoms of diabetes.
Hypophysitis	Grade 2	Withhold	
 Administer corticosteroids and initiate hormonal replacements as clinically indicated. 	
 Monitor for signs and symptoms of hypophysitis (including hypopituitarism and adrenal insufficiency)
	Grade 3 or 4	Withhold or permanently discontinue		
Hyperthyroidism	Grade 2	Continue	
 Treat with non-selective beta-blockers (e.g. propranolol) or thionamides as appropriate 	
 Monitor for signs and symptoms of thyroid disorders.
	Grade 3 or 4	Withhold or Permanently discontinue		

General instructions:				
Immune-related AEs	Toxicity grade or conditions (CTCAEv4.0)	Action taken to pembrolizumab	irAE management with corticosteroid and/or other therapies	Monitor and follow-up
Hypothyroidism	Grade 2-4	Continue	
 Initiate thyroid replacement hormones (e.g. levothyroxine or liothyroinone) per standard of care 	
 Monitor for signs and symptoms of thyroid disorders.
Nephritis and renal dysfunction	Grade 2	Withhold	
 Administer corticosteroids (prednisone 1-2 mg/kg or equivalent) followed by taper. 	
 Monitor changes of renal function
	Grade 3 or 4	Permanently discontinue		
All Other immune-related AEs	Grade 3, or intolerable/ persistent Grade 2	Withhold	
 Based on severity of AE administer corticosteroids 	
 Ensure adequate evaluation to confirm etiology or exclude other causes
	Grade 4 or recurrent Grade 3	Permanently discontinue		

NOTES:

- Withhold or permanently discontinue pembrolizumab is at the discretion of the investigator or treating physician.
- For subjects with Grade 3 or 4 immune-related endocrinopathy where withhold of pembrolizumab is required, pembrolizumab may be resumed when AE resolves to \leq Grade 2 and is controlled with hormonal replacement therapy or achieved metabolic control (in case of T1DM).

